### **Statistical Analysis Plan**

Gym class clusters of individuals will be randomly allocated to intervention groups. This approach is necessary because randomization at the individual level is impractical and we strive to avoid contamination between treatment groups. The responses from individuals within a cluster are likely to be more similar than those from different clusters because individuals within a will share a common yoga class experience. This lack of independence introduces complexity to the design and analysis. The degree of similarity, or clustering, will be quantified and reported using the intraclass correlation coefficient (ICC). When the ICC is low, individual observations contribute nearly equally to the analysis. (38). For all participants, baseline surveys (see table above) will be conducted prior to exposure to Yoga (T0). Follow-up surveys will be collected at 8 weeks (T1). Analyses will be conducted using R Version 3.6. Baseline differences between intervention and control group will be examined using independent *t* test or  $\chi^2$  test. All data will be analyzed according to treatment assignment. Two strategies will estimate treatment effects: 1) Cluster level analysis using summary measures; and 2) Individual level analysis adjusted for clustering to appropriately account for the nested structure of data and cluster randomization in

estimating. For the first, we will measure mean outcomes by cluster followed by parametric t-tests or non-parametric tests, depending on the distributions of the outcome measures. To account for the variability between gym classes and nested structure of the data, multilevel mixed-effects models will be used for each continuous outcome, with time (T0 & T1) as level 1, students as level 2, and class as level 3. To adjust for baseline pre-treatment values, explanatory variables for each outcome will include grade, gender, prior exposure to yoga at the high school, and survey time point (model 1). To assess the intervention's effect on outcomes, we will use condition (intervention or control) and the interaction between condition and time as predictors (model 2). Effect sizes (ESs) will be calculated as (estimated intervention effect)/ $\sqrt{\text{variance at student level}}$ . Interpretation of ES will determine the gains of the intervention versus control group. To calculate power for this cluster randomized trials that compares two means, we used the "clusterPower" package in R (24). Accounting for clustered design effects, 55 participants with variation in cluster sizes, an assumed low intraclass correlation of 0.001, and within-cluster variation of 5 units, this would provide at least 65% power to detect clinically meaningful effects between the treatment and control arm using two-sided tests at  $\alpha=0.05$ . To maximize test power and precision of estimation considering the few clusters in this study, we will also use wild cluster bootstrap-t procedure to correct our standard errors (9, 47).

A proxy for improved well-being, secondary academic performance outcomes, will also be analyzed descriptively pre- (during week 1) and post-intervention (at the end of week 8) (see table above).

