## Study Protocol

The second year of "A Trauma-Informed Approach for Positive Youth Development for Montana Students" will continue in the same format as winter 2020, but with 35 participants in an experimental group, along with 20 students in a control group within the same school and enrolled in classes by the same physical education teacher. District leaders wish to hold the study during the Jan-March 2021 window, as this timeframe has shown a historical spike in inappropriate student behaviors and absenteeism. Twice weekly 45-minute sessions during the 8-week intervention period will occur within two physical education classes in order to draw enough participants to gauge statistical significance with resulting data; a third physical education class with the same teacher will serve as the control group for the study, therefore creating 3 gym class clusters, which will allow for computer-generated randomization. Instead of individuals being randomly assigned, gym class clusters of individuals will be randomly allocated to intervention groups. Control group participants will also be offered 8 weeks of yoga after the study concludes.

Student incentives for at least a 75% attendance record in the experimental group include receiving a Fitbit Inspire HR for the study to track their physical health data and students will retain these to encourage healthy exercise and sleep patterns following the study. Teacher incentives for completion of surveys include classroom supply money (funneled through school administration). Gift cards will be provided to parents/guardians who complete the surveys about their child; these will be disseminated by school officials for parents to pick up at the high school, or they may be mailed by the PI on request. Control group participants will also each receive Fitbit Inspire HR upon completion of all pre- and post-survey measures as an incentive.

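### An ICC estimated from three gym classes has 1 degree of freedom net of condition, so a low reported value cannot show that clustering is small

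*Combined protocol and SAP*

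**What the plan says.** The Study Protocol section sets the design. The yoga sessions "will occur within two physical education classes", while "a third physical education class with the same teacher will serve as the control group for the study", "therefore creating 3 gym class clusters". The planned numbers are "35 participants in an experimental group, along with 20 students in a control group". How the 35 divide between the two yoga classes is not stated.

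The Statistical Analysis Plan says that clustering "will be quantified and reported using the intraclass correlation coefficient (ICC"), and adds: "When the ICC is low, individual observations contribute nearly equally to the analysis". It does not say which model or time point gives the ICC, and it plans no interval and no caveat on precision.

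The same section specifies mixed models "with time (T0 & T1) as level 1, students as level 2, and class as level 3". For the intervention effect, "we will use condition (intervention or control) and the interaction between condition and time as predictors (model 2"). Model 1 has no condition term. The power statement assumes an ICC of 0.001. The section recognises that clusters are few, but its remedy, a wild cluster bootstrap-t, is for standard errors and not for the ICC.

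**The concern.** An ICC is informative about clustering only if there are enough clusters to estimate the variance between them. Here the control arm is a single class, so its class effect cannot be separated from the arm effect. All the between-class information net of condition comes from comparing one yoga class with the other. Leaving condition out gives 2 df, but after baseline any treatment effect is then counted as clustering.

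Two things are at stake. The first is interpretation. The plan's general remark on low ICCs and the 0.001 assumed for power invite a reader to take a low estimate as confirmation, when such an estimate is common even if clustering is material. The second is the mixed model, which estimates the class variance from the same three classes. When that estimate is zero, the model treats students in a class as independent for the class-level arm contrast.

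**Working it through.** **The plan's own figures.** The only ICC in the documents is the assumed 0.001. The power of at least 65% that goes with it cannot be reproduced, because no effect size is given. Nothing below depends on it.

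**Inputs.** Three classes, two yoga and one control; 35 and 20 students (Study Protocol section). Assumed: yoga classes of 17 and 18, normal data, and true ICCs of 0.05, 0.10 and 0.20 beside the plan's 0.001.

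**Degrees of freedom.** Between classes, net of condition: 3 − 2 = 1. Within classes: 55 − 3 = 52.

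**Estimator.** The ANOVA ICC is (F − 1)/(F − 1 + n0), where F is the between-class over the within-class mean square and n0 = 35 − (17² + 18²)/35 = 17.49. An estimate r corresponds to F(r) = 1 + n0·r/(1 − r), so F(0.001) = 1.0175. For a true ICC ρ, the probability that the estimate is at or below r is the F(1, 52) distribution function at F(r)/F(ρ).

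| True ICC | F(ρ) | F(0.001)/F(ρ) | P(estimate ≤ 0.001) | P(estimate ≤ 0.01) |
|---|---|---|---|---|
| 0.001 | 1.0175 | 1.000 | 0.68 | 0.71 |
| 0.05 | 1.920 | 0.530 | 0.53 | 0.56 |
| 0.10 | 2.943 | 0.346 | 0.44 | 0.47 |
| 0.20 | 5.371 | 0.189 | 0.33 | 0.36 |

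An estimate of 0.01 or less is thus only about 1.3, 1.5 and 2.0 times as likely under 0.001 as under 0.05, 0.10 and 0.20. In the other direction, a true ICC of 0.001 gives an estimate above 0.10 in 9.5% of trials.

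**Exact interval for a reported 0.001.** The 2.5% and 97.5% points of F(1, 52) are 0.00099 and 5.328.
- Lower: 1.0175/5.328 = 0.191, which gives (0.191 − 1)/(0.191 − 1 + 17.49) = −0.05.
- Upper: 1.0175/0.00099 ≈ 1026, which gives 1025/(1025 + 17.49) = 0.98.

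**Sensitivity.**
- Yoga classes of 10 and 25: the chance of an estimate at or below 0 is 0.55 and 0.46 at true ICCs of 0.05 and 0.10, against 0.53 and 0.44 with 17 and 18.
- No condition term (2 df, n0 = 18.29): the interval for a reported 0.001 still runs from below 0 to 0.68.

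**What the difference is worth.** With mean class size 55/3 = 18.3, the design effect 1 + 17.3·ICC is 1.02 at 0.001, 1.87 at 0.05 and 2.73 at 0.10. For the arm difference, the SE relative to independence is the square root of [(1 + 16.5·ICC)/35 + (1 + 19·ICC)/20] / [1/35 + 1/20]:
- ICC 0.01: √(0.0928/0.0786) = 1.09
- ICC 0.05: √(0.1496/0.0786) = 1.38
- ICC 0.10: √(0.2207/0.0786) = 1.68

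**Consequence in a model with class as a random level.** In a simulation of follow-up data only, with a true ICC of 0.05, the class variance is estimated as zero in 53% of trials. In those trials a z-test of the arm difference has a type I error of about 17% at a nominal 5%.

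**The case against.** The strongest reply is that the plan does not act on the ICC. A reader might infer that a low ICC would let the analysts drop the cluster adjustment or prefer the individual-level strategy. The documents do not support this. Both strategies are planned, the individual-level one is itself adjusted for clustering, class stays in the model, and the bootstrap is added because clusters are few. The sentence on low ICCs is a general remark with no threshold. A reader might also infer that the ICC will be used to size year 3. The documents say only that results will help to assess the need for a year 3 expansion. Both objections stand.

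It is also fair that this is a small pilot, that reporting an ICC is good practice, that true ICCs of 0.05 to 0.20 are assumed, and that the chance of a low estimate is near one half only for true values of about 0.05 to 0.10.

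It does not follow that nothing depends on the estimate. The class variance is a component of the planned model, and a zero estimate sets the SE of the class-level arm contrast. One limit applies. The 17% comes from follow-up data only. If class enters as a random intercept alone, the condition-by-time term is a within-student contrast that does not draw on the class intercept variance. A class effect that changes over time would need its own variance component, again with 1 df net of condition. The plan does not say whether it has one.

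**Conclusion.** The point holds as one of precision and interpretation, with a practical consequence in the mixed model. The reported ICC cannot distinguish negligible from substantial clustering: an estimate at or below 0.001 is expected in 68% of trials if the truth is 0.001 and still in 53% if it is 0.05, and its interval covers nearly the whole range. It can neither confirm the planning value nor support near-independence. The percentages rest on the 17/18 split, normality and the assumed true ICCs. The width of the interval does not depend on the true ICC, and the chance of a low estimate changes little with a 10/25 split.

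This is a cheap improvement to the plan. It does not show that reporting an ICC is an error, and no wording can remove the limit set by having three classes.

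**What to change.** 1. In the Statistical Analysis Plan, where the ICC is introduced: estimate it net of condition at a stated time point, report it with an exact F-based 95% interval, and state that a low value will not be read as evidence that clustering is negligible.
2. Beside the mixed models, add a sensitivity analysis that shows the between-arm estimate with its SE and confidence interval at fixed ICCs. A grid of 0.01, 0.05 and 0.10 would serve. It is an assumed range, not one given in the documents, and the plan should say so. The SEs would be about 1.09, 1.38 and 1.68 times the independence SE. State that each interval is conditional on its fixed ICC.

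The cost is some wording, a few lines of code, and wider intervals at the larger fixed ICCs. No design change or new data are needed.

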Data will be collected in a way to best protect student privacy and confidentiality; all surveys will request that participants self-identify through a confidential code provided by the PI, and all reflective journals will be labeled with this code as well. Cortisol tubes will also be labeled with this unique code. The PI will maintain the code key in an encrypted computer file, which can only be unlocked with an access code that is known only by the PI; this computer will be kept in a locked office at all times, and all data will be securely destroyed (either by computer deletion or secure shredding) no later than one year after the conclusion of the study.

The intervention might bring up strong emotions for the participants; so too might the administration of the ACE survey during preliminary data collection. To mitigate this potential, the PI will caution students that this may occur and emphasize the importance of self-care and knowing one's own limits. Immediate referrals regarding suicidality, self-harm, depressive thoughts, etc. will be directed to the school nurse. If needed, referrals for additional, outside treatment will be provided as determined by school officials and/or requested by the participant and/or the participant's legal guardian(s). Additional resources for outside assistance will be shared with participants; these resources, along with processes for reporting and responding to adverse outcomes, can be found in the study's Human Subjects form and on student assent and parent consent forms.

Participants in this feasibility study may have reductions in severity of depression and/or anxiety as well as improvements in overall behavioral health and well-being. If needed, referrals for additional, outside treatment will be provided, as determined by school officials and/or requested by the participant and/or the participant's legal guardian(s). Benefits also include vital data to inform other potential interventions.

**Aim 1:** Pilot test a trauma-informed yoga intervention for 15-18 year-old male and female high school students.

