To prepare for pilot study year 2, feedback has been gathered from the school district, teachers, and students via focus groups and email communications to assess the burden from the various assessment instruments and participation in the pilot. Assessment measures listed below comport with this feedback. Retention and satisfaction of participants, as measured by survey instrumentation from year 1 has indicated the need for an ongoing partnership with the school district and an expansion to additional high school physical education classes (8-week intervention, n=35). During year 2, the study will compare results between the experimental group and a new 20-participant control group, which will be located within the same school setting. The intervention’s effectiveness for youth mental and physical health will be assessed with: surveys measuring depressive and anxiety symptomology; and a wearable fitness tracker (added in year 2) with cortisol testing to measure physiological changes (e.g., resting heart rate and sleep cycle patterns).

**Aim 2:** We will implement a limited feasibility study of partial online yoga delivery via Zoom within the context of the pilot study’s physical education classes to explore scalability to rural communities without access to yoga instructors as well as provide a contingency for COVID-19 school closures.

One session will be held during the PE class period with the yoga instructor teaching remotely to the entire class; another will be held outside of the regular school day with participants attending synchronously from home at a time to be determined by surveying participants’ preferences and availability; both sessions will have a 75% participation rate goal. Qualitative feedback will be gathered from both the yoga instructor and participants on their remote experiences. Remote delivery will also be provided for the control group following the conclusion of the study.

**Aim 3:** Evaluate the study’s school-community-academic partnership at the conclusion of the program using a mixed methods survey. The results will be compared using paired *t* tests with data from the same survey, collected at the end of year 1. The CAB will meet monthly to determine program adjustments. Survey administration and data analysis will occur in summer 2021. The PI will share results with the CAB to determine areas for program refinement and assess need for study continuation with a year 3 expansion.

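### With two yoga classes and one control class, the class-level tests cannot support a useful between-arm comparison, the wild cluster bootstrap does not add power, and the error rate of model 2 rests on a class effect on change that three classes cannot check

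*Combined protocol and SAP*

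**What the plan says.** The Study Protocol fixes the number of clusters. Yoga is taught in two physical education classes (35 students), and "a third physical education class with the same teacher will serve as the control group for the study, therefore creating 3 gym class clusters" (20 students). The reason given for using two yoga classes is to "draw enough participants to gauge statistical significance with resulting data". Aim 1 adds that the intervention's "effectiveness for youth mental and physical health will be assessed with: surveys measuring depressive and anxiety symptomology".

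The Statistical Analysis Plan then names three routes to a between-arm result:

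- **Class level:** "we will measure mean outcomes by cluster followed by parametric t-tests or non-parametric tests", the choice depending on the outcome's distribution.
- **Individual level:** a mixed model with time, student and class as its three levels, in which the condition-by-time interaction (model 2) carries the treatment effect. The random effects are not stated.
- **Few-cluster correction:** "To maximize test power and precision of estimation considering the few clusters in this study, we will also use wild cluster bootstrap-t procedure". The weights, whether the null is imposed, and the treatment of ties are not stated.

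Power is put at 65% or more with 55 participants, an assumed ICC of 0.001 and two-sided alpha 0.05.

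**The concern.** The plan recognises that observations within a class are not independent and that there are few clusters. It sets no limit on inference as a result. With two classes against one, the class-level tests have almost no information about between-class variation, and the single control class has none of its own. Whatever is peculiar to that class cannot be separated from condition.

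The bootstrap is presented as a way to gain power. A resampling scheme over three clusters has very few distinct outcomes, so that claim needs checking.

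Model 2 is then the likely source of any significant result. Its interaction is a comparison of change. If the model has intercepts only, class-level variation in change is left out of the standard error. The plan itself names a source of such variation: "individuals within a will share a common yoga class experience". That experience begins after baseline, so it would act on change in the yoga classes.

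At stake is how the results are read. The class-level tests would probably miss a real effect, the bootstrap could give almost any answer, and a model 2 p-value below 0.05 could be taken as evidence of effectiveness with an error rate nobody can verify.

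**Working it through.** **Inputs.** From the documents: 2 yoga classes, 1 control class, 35 and 20 students, ICC 0.001, two-sided alpha 0.05. Assumed: yoga classes of 18 and 17 (15 and 20 as an alternative), normal outcomes, no dropout, effects in student-level SD.

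**The stated 65% power.** It cannot be reproduced, because no numerical effect size is given. As a yardstick, treat students as independent: SE = √(1/35 + 1/20) = √0.0786 = 0.280 SD. The effect with 65% power is (1.960 + 0.385) × 0.280 = 0.66 SD. On three class means that effect has about 14–15% power.

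**Class-mean t-test.** df = 3 − 2 = 1, so the critical |t| is 12.71. Simulated rejection (1,000,000 trials per setting) is 4.8% under the null and 11%, 21% and 40% at 0.5, 1 and 2 SD; 65% is reached at about 3.5 SD. A Welch version cannot be computed, because one control class has no variance.

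**Class-level rank test.** There are 3 ways to choose the control class, so the smallest two-sided p is 2 × 1/3 = 0.67. A permutation test on the absolute difference stops at 1/3. Neither can reach 0.05.

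**Wild cluster bootstrap-t.** One outcome, least squares, class-clustered SE, no covariates, full enumeration (2³ = 8 two-point or 6³ = 216 six-point draws):

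| Form | Yoga split | Weights | Smallest p | Size | Power at 1 SD |
|---|---|---|---|---|---|
| Null imposed, ties counted | 18/17 | two-point | 0.25 | 0% | 0% |
| Null imposed, ties counted | 18/17 | six-point | 0.056 | 0% | 0% |
| Null imposed, ties not counted | 18/17 | two-point | 0 | 35% | 93% |
| Null imposed, ties not counted | 18/17 | six-point | 0.028 | 2.6% | 9.5% |
| Unrestricted | 18/17 | either | 0 | 3.5% | 13% |
| Unrestricted | 15/20 | two-point | 0 | about 15% | about 60% |
| Unrestricted | 15/20 | six-point | 0 | about 3% | about 12–15% |

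With three simulated covariates in the one-outcome regression, the null-imposed, ties-counted, six-point form has a smallest p of about 0.03 and rejects in under 1% of null trials. The unrestricted form's size rises to about 24–30%. A stacked T0/T1 version of condition × time without covariates (18/17, assumed pre-post correlation 0.5) gave the same pattern as the 18/17 rows.

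**Model 2 with random intercepts only.** Class and student intercepts cancel from T1 − T0, so the interaction equals the difference in mean change. With the student-level variance of change set to 1, the model's variance is 1/35 + 1/20 = 0.0786. The true variance adds k·τ², where τ² = ρ/(1 − ρ) and ρ is the ICC of change. If only the yoga classes vary, k = 1/2; if all three vary, k = 1/2 + 1 = 1.5. The SE is too small by the factor w = √(1 + kτ²/0.0786), and type I error = 2Φ(−1.96/w).

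Example, ρ = 0.01: τ² = 0.0101. For k = 1.5, w = √(1 + 0.01515/0.0786) = 1.09 and type I error = 2Φ(−1.795) = 7.3%.

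| ICC of change (assumed) | k = 0.5: w, type I | k = 1.5: w, type I |
|---|---|---|
| 0.001 | 1.00, 5.1% | 1.01, 5.2% |
| 0.005 | 1.02, 5.4% | 1.05, 6.1% |
| 0.01 | 1.03, 5.7% | 1.09, 7.3% |
| 0.05 | 1.16, 9.0% | 1.42, 16.6% |

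Simulated t-tests on individual changes agree: 5.0%, 5.7% and 8.6% (k = 0.5) and 5.2%, 7.1% and 16.0% (k = 1.5) at 0.001, 0.01 and 0.05. At 0.001, power is about 42% and 94% at 0.5 and 1 SD of change.

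**The case against.** The best defence is that this is a pilot: "Participants in this feasibility study may have reductions in severity of depression and/or anxiety" is how the Study Protocol describes the expected benefit, and the plan says gains will be judged from effect sizes. It also commits to reporting the ICC. All students are "enrolled in classes by the same physical education teacher" in one school, which makes a low class effect more plausible. These points stand, and they lower the seriousness. They do not remove the stated alpha, the stated power or the aim of gauging significance.

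Four stronger readings are tempting, and the documents do not support them:

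- **The class-mean t-test is invalid.** It is not; it holds its size (4.8%). Its fault is low power.
- **The bootstrap can never reject.** That is true only with the null imposed, ties counted and no covariates. The plan specifies covariates and is silent on the other two.
- **Model 2 is sound only if the ICC of change is about 0.001.** At 0.01 its type I error is still 5.7–7.3%. Larger inflation needs an ICC near 0.05, which is an assumption; the documents give no ICC of change. Random intercepts only is also one reading of a plan that does not say.
- **The 65% figure was computed for a different number of classes.** Without an effect size or the class numbers used, this cannot be established.

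**Conclusion.** The point holds and should be fixed, but it does not undermine the pilot. That the t-test has 1 df and the rank test cannot go below 0.67 follows from the design alone. The power figures for the t-test assume classes of 18/17/20, ICC 0.001 and normal outcomes.

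The claim that the bootstrap increases power is wrong for every form tested: size ran from 0% to about 35%, and every form with size at or below 5% had at most about 15% power at 1 SD. Those figures depend on weights, null imposition, tie rule, the split of the 35 yoga students and covariates. Bootstrapping the full three-level model was not evaluated.

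Model 2 is the only planned analysis shown to combine near-nominal size with useful power, and it does so only if the ICC of change is small. Whether only the yoga classes vary or all three do is a further assumption. Three classes cannot settle either question.

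**What to change.** In the Statistical Analysis Plan:

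1. Delete the non-parametric class-level test and the statement that the bootstrap improves power and precision. Do not use the wild cluster bootstrap as a hypothesis test. If it is kept, state its weights, null imposition and tie rule, and label it exploratory. If the class-mean t-test is kept, specify the pooled version and label it as 1 df with very low power. Show the three class means and mean changes.
2. State the mixed model's random effects, and that condition is confounded with the single control class. Report model 2 as an estimate with a 95% CI conditional on these three classes. Say that p < 0.05 alone will not be treated as evidence of effectiveness.
3. For the anxiety and depression scales, add one or two sensitivity CIs using SE² + k·τ²·(student-level variance of change). ICCs of change of 0.01 and 0.05 would serve: they widen the interval by about 1.03–1.09 and 1.16–1.42, depending on whether only the yoga classes or all classes vary.

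The cost is wording and a few lines of code, with no added students or classes. The study gives up a significance claim that three classes cannot support, and the sensitivity intervals are somewhat wider.

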### ***Salivary Cortisol Assays.***

Students in both the experimental and control groups will be administered cortisol testing at the beginning of weeks 1 and 4 and the conclusion of week 8, each time prior to the yoga session (or at the beginning of their physical education class, if in the control group). Specifically, students will provide a saliva sample to the school nurse or PI, to be deidentified (using a code key system) before analysis by the CAIRHE Translational Biomarkers Core Lab at MSU. Testing will use the Abcam (ab154996) cortisol in vitro competitive ELISA (Enzyme-Linked Immunosorbent Assay) kit designed for accurate quantitative measurement of cortisol in saliva (sensitivity 0.12 ng/ml). Deidentified cortisol data will be returned to the PI for re-identification using the code key. Comparisons using paired t tests will assess trends and determine usefulness of this measure.

---

 If we increase  $\alpha$  to 0.1, we can reduce the probability of a **Type II error** and increase our power to 0.86 but we are also more likely to commit a **Type I error** (rejecting a true null hypothesis).

Using deidentified participant codes (with the PI retaining access to the code key system), data will be triangulated through observational data, qualitative remarks in participant journals, pre- and post-survey data, heart rate and sleep cycle data, cortisol analyses, and secondary academic and behavioral data.

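### Model 2 is said to adjust for baseline, but it neither conditions on the T0 outcome nor gives the arms a common T0 mean, so condition-by-time compares raw change

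*Combined protocol and SAP*

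**What the plan says.** The individual-level analysis in the Statistical Analysis Plan is a three-level mixed model, "with time (T0 & T1) as level 1, students as level 2, and class as level 3". The covariates of model 1 are introduced by a statement of purpose: "To adjust for baseline pre-treatment values, explanatory variables for each outcome will include grade, gender, prior exposure to yoga at the high school", followed by survey time point. For the treatment effect, "we will use condition (intervention or control) and the interaction between condition and time as predictors (model 2".

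Nothing else in the plan adjusts for the T0 outcome. Baseline differences between arms are to be tested, but no action follows from the result. The cluster-level strategy compares class means, and no baseline adjustment is described for it.

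The power statement assumes "an assumed low intraclass correlation of 0.001, and within-cluster variation of 5 units" and claims "at least 65% power to detect clinically meaningful effects". The footnote says that relaxing alpha to 0.1 would "increase our power to 0.86".

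**The concern.** The stated purpose and the listed terms do not match. Grade, gender and prior yoga are student characteristics, and none of them is the pre-treatment value of the outcome. They also take the same value at T0 and T1. Entered as main effects, they cancel out of the condition-by-time contrast when data are complete, so the adjustment that is named leaves the treatment estimate where it was.

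Two things are at stake. With 55 students, precision is lost if the class ICC is as low as the plan assumes. And if one arm happens to start worse, regression to the mean makes it appear to gain more, which is credited to or held against yoga. The footnote considers a higher Type I error rate to gain power, while T0 data that are already to be collected are not fully used.

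**Working it through.** **Inputs.** 35 intervention and 20 control students in three classes, two against one (Study Protocol). ICC 0.001 (Statistical Analysis Plan). Assumed: the 35 split as 17 and 18; equal variances at T0 and T1; a class effect that is stable over time; complete data; r = 0.5 or 0.7. The measures table gives instrument reliabilities, not an 8-week correlation in this sample. All results are in within-class SD units.

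**The plan's own figure.** The 65% power cannot be reproduced, because no effect size is stated. Solving backwards by normal approximation: SE = sqrt(1.0165/35 + 1.019/20) = 0.283 SD, and (1.960 + 0.385) x 0.283 = 0.66 SD. That effect would give 76% power at alpha 0.10, not 86%. A t distribution with 2 df gives 87%, at an effect of about 1.28 SD. This is a separate matter, but it shows that the 65% cannot be tied to a change score.

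**Step 1: what condition by time estimates.** A mixed model with a student intercept, a time-constant covariate, time, condition and condition by time was fitted to simulated complete data. The interaction was 0.1171 and the difference in mean change was 0.1171.

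**Step 2: shift given a T0 imbalance.** Let k = 1/35 + 1/20 = 0.0786. The chance T0 difference has SE sqrt(k) = 0.28 SD, so an imbalance of 0.3 SD is ordinary. Given imbalance d, the change estimate moves by -(1-r)d:
- r = 0.7: 0.3 x 0.3 = 0.09 SD
- r = 0.5: 0.5 x 0.3 = 0.15 SD

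Simulation at ICC 0.001 (40,000 trials) gave -0.49 (r = 0.5) and -0.30 (r = 0.7) per unit of imbalance, against about 0 after T0 adjustment.

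**Step 3: precision with no class effect.**
- Change: 2(1-r)k = 0.0786 (r = 0.5) and 0.0471 (r = 0.7).
- T0-adjusted: (1-r^2)k = 0.0589 and 0.0401.
- Ratio: (1+r)/2 = 0.75 and 0.85.

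Simulated student-level ANCOVA at ICC 0.001, with the slope estimated, had variances of 0.060 against 0.078 (ratio 0.77) and 0.041 against 0.047 (ratio 0.87).

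**Step 4: dependence on the class ICC.** Let s = ICC/(1-ICC). Two classes against one contribute 1.5s to the variance of an arm difference.
- Change: unaffected, 2(1-r)k.
- Shared T0 mean, class variance known: V(1-b^2), with V = 1.5s + k and b = (1.5s + rk)/V.
- Shared T0 mean, class variance taken as zero: (1-r^2)k + 1.5(1-r)^2 s. ANCOVA on T1 has the same form, plus a little for the estimated slope.

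| ICC (s) | r | Change | Shared mean, known | Shared mean, taken as zero |
|---|---|---|---|---|
| 0.001 (0.0010) | 0.5 | 0.079 | 0.059 | 0.059 |
| 0.001 | 0.7 | 0.047 | 0.040 | 0.040 |
| 0.05 (0.0526) | 0.5 | 0.079 | 0.069 | 0.0589 + 0.0197 = 0.079 |
| 0.05 | 0.7 | 0.047 | 0.044 | 0.0401 + 0.0071 = 0.047 |
| 0.10 (0.1111) | 0.5 | 0.079 | 0.072 | 0.0589 + 0.0417 = 0.101 |
| 0.10 | 0.7 | 0.047 | 0.045 | 0.0401 + 0.0150 = 0.055 |

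Break-even for the last column and for ANCOVA: 1.5(1-r)^2 s = (1-r)^2 k, so s = 0.0786/1.5 = 0.0524 and ICC = 0.0524/1.0524 = 0.05, for any r. Simulated ANCOVA at ICC 0.10 had variance 0.101 against 0.079 (r = 0.5) and 0.057 against 0.047 (r = 0.7).

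**The case against.** The case for leaving the model alone has real substance.

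- **T0 is already in the model.** A reader might infer that the analysis ignores baseline outcome values. It does not: each T0 score is a response and is subtracted in the contrast. What is missing is a T0 covariate or a common T0 mean. The introductory phrase may also have meant student characteristics; in that case the wording is loose, but the T0 outcome is still not adjusted for.
- **The change estimate is legitimate.** A reader might infer that chance imbalance passes straight into the effect, or that the estimate is biased. Neither follows. The imbalance is subtracted in full, which over-corrects and leaves a (1-r) share of opposite sign. That shift is conditional on the observed imbalance, and over the randomisation the estimate is unbiased.
- **Change scores cancel stable class differences.** The plan itself expects students in a class to resemble one another. Above an ICC of about 0.05, student-level ANCOVA is the less precise choice. At ICC 0.10 it also moves with the imbalance, by +0.32 (r = 0.5) or +0.20 (r = 0.7) per unit, against -0.16 or -0.09 for the change score. This objection stands, and it is why ANCOVA is not the preferred fix.
- **This is a pilot with one control class.** The number of clusters limits inference far more than the choice of baseline adjustment, and no version of model 2 cures that. This also stands, and it limits the importance of the point.

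**Conclusion.** The point holds in this form: the plan states a baseline adjustment that its model does not make, and condition by time is a difference in raw change. At the plan's own ICC of 0.001 that estimate is less precise than one adjusted for T0. The adjusted variance is about 0.77 (r = 0.5) or 0.87 (r = 0.7) of it with ANCOVA, and about 0.75 or 0.85 with a shared T0 mean. An ordinary 0.3 SD imbalance shifts it by 0.09 to 0.15 SD.

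These sizes rest on an assumed r, equal variances, complete data and a stable class effect. Class differences that arise only by T1 would add the same variance to every estimator considered here.

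A reader might go on to infer a specific power gain from the 65%. The documents do not support one: they give no effect size and no r, they do not tie the 65% to a change score, and there are only three clusters.

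**What to change.** Keep the three-level T0/T1 model with its covariates and class term. In model 2, remove the condition main effect so that both arms share one T0 mean, and take condition by time as the treatment effect. Specify the term as condition multiplied by a 0/1 indicator for T1; an interaction with time as a factor can silently restore a separate T0 difference. Class randomisation, and T0 collection before exposure to yoga, justify the constraint. Keep the cluster-level comparison and the wild cluster bootstrap. Report the unconstrained change-score estimate as a sensitivity analysis, together with the estimated class variance, and state the assumed r.

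If ANCOVA on T1 is preferred, present it as an alternative and not an equivalent: it loses its advantage near ICC 0.05 and is less precise than the change score above that.

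The cost is a few lines of SAP wording and one extra fit per outcome, with no new data. The downside should be stated: three classes can barely estimate the class variance. If the model takes it as zero, the gain is essentially gone at a true ICC of 0.05 and has reversed by 0.10, which is why the unconstrained estimate should be shown beside it.
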